A variety of genetic diseases of lymphohematopoiesis have been effectively treated and either cured or ameliorated by allogeneic HSCT from an HLA-matched histocompatible healthy sibling [45, 46]. The conditioning regimen of myeloablative high dose Busulfan along with immunoablative high-dose cyclophosphamide (BU- CY) ± antithymocyte globulin (ATG) was developed in the 1980's after important clinical studies were conducted to better understand the prerequisites for replacement of hematopoietic stem cells (HSC) carrying deleterious mutations with those derived from matched healthy donors [46]. These studies established that, in the setting of histocompatible transplant, ablation of host hematopoietic stem cells with high-dose BU (16 mg/kg, 600 mg/m2, or 640 mg/m2) and of host immunity with CY ± ATG allowed durable engraftment of donor HSCs.

[figure not shown]
Since most patients lack a histocompatible sibling donor, a major challenge in the treatment of the genetic lymphohematological disorders is the development of HSCT regimens that result in high levels of engraftment while avoiding regimen-related toxicity and GVHD. Higher risks of graft rejection and GVHD with the use of alternative donors, including unrelated donors (URD), mismatched related donors (mMRD), umbilical cord blood units, and haplo-identical donors, makes these transplants high risk and are associated with high rates of TRM as well. Consequently, the results of HSCT for patients with genetic disorders, using alternative donors has been both limited and suboptimal [47-54].

Given the especially increased risk of rejection with haploidentical transplants in patients with non-malignant disorders [52,54], we are proposing the use of additional immunosuppression to the standard back-bone of Busulfan/cyclophosphamide/anti- thymocyte globulin, by adding Fludarabine.

Miltenyi supported a Phase II multi-center clinical trial sponsored by the BMT CTN (BB-IDE 11965) which enrolled 47 AML patients from October 2005-December 2008 Evaluated the use of the CliniMACS® CD34 Reagent System for selecting CD34+ cells from HLA-matched related donors for allogeneic stem cell transplantation after myeloablative therapy in patients with Acute Myeloid Leukemia (AML) in 1st or 2nd CR, without additional GvHD prophylaxis

Post processing outcomes in all centers were able to process grafts that met the study criteria.

[figure not shown]
- All patients received the minimum CD34+ dose (> 2.0 x 10⁶ cells/kg)

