- 84.1% of patients received > 5 x 10⁶ CD34+ cells/kg

Final Cellular Product Summary

Parameter	Result
Median CD34⁺ dose	7.92 x 10 ⁶ /kg
Range	2.4 - 30.3 x 10 ⁶ /kg
Median CD3+ dose	0.7 x 10 ⁴ /kg
Range	0.1 – 8.3 x 10 ⁴ /kg
Median Log ₁₀ TCD	4.9 logs
Range	3.2 – 5.9 logs

- All Gram stains/14 day cultures were negative
- All endotoxin < 5.0 EU/kg
- No significant infusion related toxicities observed

Primary Endpoint 6 Month Disease-Free Survival of >75%

The BMT CTN 0303 conclusions was that HCT following myeloablative preparative regimen for patients with AML in CR1 or CR2 can be performed in a multicenter setting using the CliniMACS® CD34 Reagent System without additional post-transplant pharmacologic GvHD prophylaxis

All 1° and most 2° endpoints were met, demonstrating:

- 81.8% Disease-Free Survival 6 months post TX
- No primary graft failure; consistent neutrophil and platelet engraftment
- Acute GvHD grades II-III <23%. No Grade IV aGvHD
- Chronic GvHD at 2 years 19%; extensive 6.8%
- TRM <20% at 2 years
- Overall risk of relapse was low at 23.7% at 2 years

The CliniMACS® CD34 Reagent System consistently produced a graft with > 2×10^6 CD34+ cells/kg and < 1×10^5 CD3+ cells/kg with no reported device related toxicities.

In January, 2014, the CliniMACS[®] CD34 Reagent System received FDA approval as a Humanitarian Use Device for processing hematopoietic progenitor cells collected by apheresis from an allogeneic, HLA-identical, sibling donor to obtain a CD34+ cell-enriched population for hematopoietic reconstitution following a myeloablative preparative regimen without the need for additional GvHD prophylaxis in acute myeloid leukemia.(44)

In summary, the use of CD34+ selected PBSC and manipulated bone marrow grafts without post-transplant GvHD prophylaxis for children was associated with rapid engraftment, low 100-day mortality, very low incidence of severe GvHD, and excellent survival. The overall survival compares favorably with matched-related and URD HSCT. Immune reconstitution was slow and post-transplant infections contributed to morbidity and mortality.

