10.2 Stopping Rules

The study includes stopping rules based on the incidence of graft failure (or graft rejection), and acute GVHD.

Stopping rule for primary graft failure: The first 30 enrolled patients (related and unrelated) will be evaluated for the stopping rule for primary graft failure. The trial is stopped if there are \geq b graft failures out of k resolved patients. Only points where stopping is possible are listed.

k	2	4	5	6	8	9	10	12	13	14	15	16	18	19	20	21	23	24	25	26	27	28	30
b	2	3	3	3	4	4	4	5	5	5	5	5	6	6	6	6	7	7	7	7	7	7	8

The stopping rule for graft failure yields the probability of stopping the trial of 0.05 if the rate of graft failure is 0.1. The probability of stopping the trial is 0.41 if the graft failure rate is 0.2, 0.82 if the graft failure rate is 0.3, and 0.96 if the graft failure rate is 0.4.

These probabilities were calculated based on the binomial distribution. The stopping rule was generated as described by Ivanova et al. (40).

If the study reaches a stopping boundary, the study will be suspended. At this point it may be terminated by the PI or submitted to the safety monitor with a description of the failures to date and a rationale for why the study should be continued. Proper use of the stopping rule table will be ensured by the Study Investigator.

Stopping rule for Grade \geq IV toxicity: If any patient develops grade \geq IV acute GvHD, grade \geq IV infection, or any unexpected grade \geq IV toxicity by 4 weeks post-transplant, the protocol will be halted and the processing reevaluated before proceeding.

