12 STATISTICAL CONSIDERATIONS

Interim descriptive analyses will be performed annually. As the eligibility for this protocol is very broad, analyses will be done separately for several pre-specified subgroups.

First, analyses will be conducted separately for patients transplanted for malignant diseases and those transplanted for non-malignant diseases. They will also be analyzed separately for transplants using mismatched related versus alternative donors. Finally, analyses will be conducted separately for primary vs. secondary allogeneic transplants. Further separation of the study population such as adults vs. pediatrics and myeloablative vs. non-myeloablative conditioning regimens will be considered depending on the patient numbers. In particular, neutrophil and platelet engraftment will only be analyzed using transplants with myeloablative conditioning regimens.

Baseline characteristics will be described using frequencies/percent or median/range as appropriate.

The study will enroll 30 transplant recipients at Stanford. As the recommended prescription of allogeneic transplantation for different underlying diseases grows, enrollment on this protocol is expected to gradually increase in relation to the overall number of transplants performed in our center.

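### The graft-failure boundary has no donor-type stratum, and its stated stopping probabilities hold only if all 30 recipients share one failure rate

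*Combined protocol and SAP*

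**What the plan says.** Section 10.2, repeated in the synopsis, defines who is monitored: "The first 30 enrolled patients (related and unrelated) will be evaluated for the stopping rule for primary graft failure". The trial stops on reaching at least "b graft failures out of k resolved patients", using one table of k and b that runs from k = 2 to k = 30. Its operating characteristics are given for a common rate only: the rule "yields the probability of stopping the trial of 0.05 if the rate of graft failure is 0.1", then "0.41 if the graft failure rate is 0.2, 0.82 if the graft failure rate is 0.3", and "0.96 if the graft failure rate is 0.4". Crossing the boundary suspends the study. The principal investigator may then terminate it or put a case for continuing to the safety monitor.

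The eligibility criteria (3.1) admit matched as well as mismatched donors, and section 2.4 allows matched recipients with borderline organ function. Neither gives a planned share or a cap.

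Section 2.1 treats donor type as relevant to engraftment. For the HLA-matched AML trial it reports "No primary graft failure; consistent neutrophil and platelet engraftment". For one mismatched setting it introduces extra immunosuppression with the words "Given the especially increased risk of rejection with haploidentical transplants in patients with non-malignant disorders". Section 12 states that "As the eligibility for this protocol is very broad, analyses will be done separately for several pre-specified subgroups", and one of its splits is by donor category. Those analyses are annual and descriptive, and none feeds the boundary.

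**The concern.** A boundary on a pooled count responds to the average failure rate of those enrolled. Each low-risk matched recipient who engrafts moves k forward without adding a failure, so the mismatched group needs more failures before the table is crossed. A reader of section 10.2 could take 0.82 as the protection that mismatched recipients have if they lose grafts at 30%. That is correct only if nearly all of the 30 are mismatched, or if matched recipients fail as often.

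No other numeric trigger clearly covers this. Section 8.2 lists graft failure among the expected toxicities of transplantation, so the halt for unexpected grade IV toxicity would not plainly catch it.

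**Working it through.** **Inputs from the documents.** The k/b table, 30 patients, and the scenario rates 0.1 to 0.4 come from section 10.2. Background rates come from section 2.1: no primary graft failure in the matched AML trial of 47 patients; 91% primary engraftment in one mismatched series (about 9% failure); in the other, 1 primary failure among 18 (6%) plus 2 immunological rejections, so 3/18 = 17% if rejections count.

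**Assumptions.** The donor mix and the matched failure rate are not in the documents. The matched rate is varied over 0, 2%, 5% and 10%. The mismatched rate is set at 30%, one of the protocol's own scenarios. Enrolment order is random.

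**Method.** Let q_k(x) be the probability of x failures among k resolved patients with no stop so far, and p_k the failure rate of patient k. Then q_k(x) = (1 − p_k)·q_{k−1}(x) + p_k·q_{k−1}(x−1). At each listed k, the probability at x ≥ b is moved to stopped. Mixed cohorts are averaged over random enrolment orders.

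**Step 1: the plan's own figures.** With one common rate:

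| Rate | Stated | Recomputed |
|---|---|---|
| 0.1 | 0.05 | 0.049 |
| 0.2 | 0.41 | 0.408 |
| 0.3 | 0.82 | 0.827 |
| 0.4 | 0.96 | 0.978 |

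All four agree within 2 percentage points, so the table is being read as intended.

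**Step 2: pooled rule, mismatched recipients at 30%.** Probability of stopping, by matched failure rate:

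| Mismatched of 30 | 0 | 2% | 5% | 10% |
|---|---|---|---|---|
| 27 | 0.73 | 0.74 | 0.75 | 0.77 |
| 24 | 0.61 | 0.63 | 0.65 | 0.69 |
| 20 | 0.41 | 0.44 | 0.49 | 0.58 |
| 15 | 0.17 | 0.21 | 0.28 | 0.41 |
| 10 | 0.03 | 0.06 | 0.12 | 0.24 |

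Every entry is below 0.82. As a rough check, a 15/15 mix at 30% and 2% averages 0.5 × 0.30 + 0.5 × 0.02 = 0.16, and a common rate of 0.16 gives 0.22.

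**Step 3: where stopping becomes less likely than not.** The pooled rule has a 50% chance of stopping at a common rate of 0.219. The mismatched share that produces this average is (0.219 − m)/(0.30 − m) for matched rate m:

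- m = 0: 0.219/0.30 = 73%
- m = 0.02: 0.199/0.28 = 71%
- m = 0.05: 0.169/0.25, about 67%
- m = 0.10: 0.119/0.20, about 59%

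So the rule is more likely silent than not only if matched recipients make up at least roughly 27% to 41% of the 30.

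**Step 4: how much is pooling.** The same table applied only to mismatched recipients at 30% stops with probability 0.55 for 15 recipients, 0.67 for 20 and 0.73 for 24. At 15/15, the fall from 0.83 to 0.55 is therefore the effect of fewer mismatched recipients. The further fall from 0.55 to 0.21–0.28 (matched failure 2% to 5%) is the effect of pooling.

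**Step 5: either boundary.** If crossing the pooled or the mismatched-only boundary suspends the study, the 15/15 stopping probability is 0.55 with matched failure at 2% and 0.56 at 5%. If both groups fail at 10%, the either-boundary false-stop probability at 15/15 is 0.067, against 0.049 for the pooled rule alone.

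**The case against.** A single pooled boundary is a legitimate choice in a 30-patient, single-arm access study, and the size of the effect rests on a mix the documents do not give. Section 2.4 presents alternative-donor recipients as the main population and mentions matched recipients only with borderline organ function, which suggests a mainly mismatched cohort. The 30% rate is a design scenario, well above the 6% to 9% primary failure (17% counting rejections) in the protocol's own mismatched series. The matched trial with no failures enrolled AML in remission after myeloablative conditioning, whereas matched recipients here may differ, so a rate near 2% is not secure. The investigator also reviews safety data and may terminate the study, and annual subgroup summaries are planned.

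Most of this stands, and it limits the claim. A reader might infer that the boundary will mostly stay silent when mismatched recipients lose grafts at 30%. The documents do not support that: it needs at least roughly 27% to 41% matched recipients, and with 24 of 30 mismatched the rule still stops more often than not. Nor can the whole gap from 0.82 be put down to dilution, as Step 4 shows. Two supporting texts should also not be over-read. The words on related and unrelated patients concern relatedness, so the pooling of matched with mismatched follows from monitoring the first 30 enrolled together with the eligibility criteria. And section 12 contrasts mismatched related with alternative donors, which is not a matched-versus-mismatched split.

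What the objection does not remove is that the stated probabilities describe only a common rate. Discretionary review and annual summaries are not a boundary with known properties.

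**Conclusion.** The point holds in conditional form. The boundary has no donor-type stratum, and 0.82 at a 30% failure rate describes mismatched recipients only if the cohort is close to uniform in risk. With an even split and matched failure of 2% to 5%, the figure is about 0.21 to 0.28, of which the part below 0.55 is attributable to pooling. With 24 of 30 mismatched it is about 0.61 to 0.69 for matched failure of 0 to 10%. The direction is the same in every mix tried; the size depends on the assumed mix, the assumed matched rate and the 30% scenario. This is a worthwhile, inexpensive improvement to the rule, not an error in its arithmetic, which reproduces.

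**What to change.** Keep the pooled rule and add to section 10.2 and the synopsis: the same k/b table is also applied to recipients of mismatched donors counted alone, with mismatched defined by the HLA criterion used at enrolment; crossing either boundary suspends the study for the review already described. State the resulting stopping probabilities for a range of donor mixes and failure rates, and label the existing four figures as applying to a common rate.

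The cost is a few sentences, with no extra patients or data. The false-stop probability rises from 0.05 to about 0.067 at a 15/15 split if both groups fail at 10%, and a false crossing leads to suspension and review, not automatic termination. The change does not overcome small numbers: with only 10 mismatched recipients, their own count stops with probability about 0.41 at a 30% rate.

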11 REGULATORY CONSIDERATIONS

11.1 Institutional Review of Protocol

The protocol, the proposed informed consent and all forms of participant information related to the study will be reviewed and approved by the Stanford IRB and other regulatory groups as necessary and required. Any changes made to the protocol will be submitted as a modification and will be approved by the IRB prior to implementation. The Protocol Director will disseminate the protocol amendment information to all participating investigators.

11.2 Data Management Plan

The PI, or his/her designee, will prepare and maintain adequate and accurate participant case histories with observations and data pertinent to the study. Study specific Case Report Forms (CRFs) will document treatment outcomes for data analysis. Case report forms will be developed using the REDCap database system and will be maintained by the SCT clinical research nurse and/or program's CRA.

12 STATISTICAL CONSIDERATIONS

Interim descriptive analyses will be performed annually. As the eligibility for this protocol is very broad, analyses will be done separately for several pre-specified subgroups.

First, analyses will be conducted separately for patients transplanted for malignant diseases and those transplanted for non-malignant diseases. They will also be analyzed separately for transplants using mismatched related versus alternative donors. Finally, analyses will be conducted separately for primary vs. secondary allogeneic transplants. Further separation of the study population such as adults vs. pediatrics and myeloablative vs. non-myeloablative conditioning regimens will be considered depending on the patient numbers. In particular, neutrophil and platelet engraftment will only be analyzed using transplants with myeloablative conditioning regimens.

Baseline characteristics will be described using frequencies/percent or median/range as appropriate.

The study will enroll 30 transplant recipients at Stanford. As the recommended prescription of allogeneic transplantation for different underlying diseases grows, enrollment on this protocol is expected to gradually increase in relation to the overall number of transplants performed in our center.

APPENDIX A: Graft-Versus-Host Disease Grading

The modified Keystone criteria will be used for acute GvHD scoring for both pediatric and adult participants. See tables below.

If the criteria are not met but clinical signs and symptoms are consistent with GvHD and systemic therapy was begun, then the diagnosis of acute GvHD can be made. The staging of acute GvHD in the affected organ will be determined by the scoring team based on the severity of symptoms using the NIH Consensus Organ Scoring System of chronic GvHD, as a guide.

The onset date for acute GvHD will typically be the date when the systemic immunosuppression is added or escalated.

When acute GvHD progresses directly to chronic GVHD and a definite onset date cannot be determined, d+100 will be used for the onset date of chronic GvHD.

The diagnosis of acute or chronic GvHD will typically be based on clinical signs and symptoms and are not based on the time of symptoms after transplant or donor lymphocyte infusion (DLI).

The NIH Consensus recommendations will be used to establish the diagnosis of chronic GVHD:

Distinction from acute GvHD;

At least one diagnostic sign **OR** at least one distinctive sign confirmed by biopsy or other tests; Exclusion of other diagnosis.

Chronic GvHD stated as suspected, presumed, and possible or not meeting the NIH consensus criteria be reviewed at the team's weekly patient meetings.

Signs and Symptoms described as:	Chronic GvHD?
Inactive or Quiescent	No
Irreversible symptoms present	Yes
No symptoms, patient on GvHD therapy	No

Article I. Acute GvHD Grading

Grade	Skin	Liver	Gut
0	None	None	None
1	Stages 1 - 2	None	None
2	Stage 3, or	Stage 1, or	Stage 1
3		Stages 2 - 3, or	Stages 2 - 4
4*	Stage 4, or	Stage 4	

 Grade 4 may also include lesser organ involvement but with an extreme decrease in performance status.

Article II. Acute GvHD Staging

Stage*	Skin [†]	Gut (adults) ^{§¶}	Gut (children) §¶	Liver [‡]
0	No evidence of GvHD	< 500 mL/d diarrhea	< 10 mL/kg/d diarrhea	T.bili < 2.0 mg/dL
1	< 25% body surface area involved	500 - 999 mL/d diarrhea, or persistent nausea with histologic evidence	10 - 15 mL/kg/d diarrhea, or persistent nausea with histologic evidence	T.bili 2.0 - 3.0 mg/dL
2	25% - 50%	1000 - 1499 mL/d diarrhea	16 - 20 mL/kg/d diarrhea	T.bili 3.1 - 6.0 mg/dL
3	> 50%	>/= 1500 mL/d diarrhea	21 - 25 mL/kg/d diarrhea	T.bili 6.1 - 15.0 mg/dL
4	With bullous formation	Severe abdominal pain with/without ileus	> 26 mL/kg/d diarrhea	T.bili > 15.0 mg/dL

- Criteria for grading minimum degree of organ involvement required conferring that grade.
- † Use "rule of nines" or burn chart to determine extent of rash.

Range given as total bilirubin level.

- § Volume of diarrhea applies to adults. For pediatric patients, the volume of diarrhea should be based on body surface area.
- ¶ Persistent nausea with histologic evidence of GVHD in the stomach or the duodenum.

Article III. Chronic Graft-versus-Host Disease Grading

ONSET:

- De Novo no prior aGVHD
- Interrupted prior aGvHD resolved before onset of cGvHD
- Progressive prior aGvHD did not resolve before onset of cGvHD

GRADE:

Limited – localized skin involvement and/or hepatic dysfunction due to cGvHD Extensive – one or more of the following:

- generalized skin involvement; or
- liver histology showing chronic aggressive hepatitis, bridging necrosis or cirrhosis; or
- involvement of eye: Schirmer test with < 5 mm wetting; or
- involvement of minor salivary glands or oral mucosa demonstrated on labial biopsy; or
- involvement of any other target organ

SEVERITY:

- Mild signs and symptoms of cGvHD do not interfere substantially with function and do not progress once appropriately t treated with local therapy or standard systemic therapy (corticosteroids and/or cyclosporine or FK 506)
- Moderate signs and symptoms of cGvHD interfere somewhat with function despite appropriate therapy or are progressive through first line systemic therapy (corticosteroids and/or cyclosporine or FK 506)
- $\bullet \quad \text{Severe} \text{signs and symptoms of cGvHD limit function substantially despite appropriate therapy or are progressive through second line therapy}\\$

APPENDIX B: Current Criteria Used at Stanford University at the Adult and Pediatric Programs Stem Cell Transplantation Programs to establish Graft Failure

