Subject Population	Pediatric and adult patients up to 35 years old, of any gender, and ethnic background, with malignant and/or non-malignant diagnosis that are treatable though allogeneic stem cell transplantation.

Inclusion Criteria:

- Participants greater than one month of age.
- Participant has a disorder that can be treated with a hematopoietic stem cell transplant
 - Participant's is eligible for an allogenic HSCT as per current institutional SOP and FACT standards
- Participant must have a related or unrelated matched or mismatchedrelated donor who is:
 - Able to receive granulocyte colony-stimulating factor (G-CSF) and undergo apheresis either through placement of catheters in antecubital veins or a temporary central venous catheter OR agrees on a bone marrow harvest;
 - Healthy as per donor selection screening (following current SOP based on standards of foundation for accreditation of cellular therapy and stem cell transplantation – FACT);
 - Willing to participate and sign consent.
- Participant or Legal Authorized Representative is able to sign informed consent (and signed assent, if applicable) for transplant.

Exclusion Criteria:

- Participant does not qualify for an allogeneic transplant due to medical screening, underlying disease, or lack of alternative donors.
- Any condition that compromises compliance with the procedures of this protocol, as judged by the principal investigator.

Principal Investigator will evaluate and report all grade 3 or 4 adverse reactions that are unexpected and possibly related to the investigation in process and are not expected TRM as per protocol definition. If it becomes clear that the study treatment is less effective than other available treatments or the toxicity is unacceptable we will follow the stopping rules.

Stopping rule for primary graft failure: The first 30 enrolled patients (related and unrelated) will be evaluated for the stopping rule for primary graft failure. The trial is stopped if there are ≥ b graft failures out of k resolved patients. Only points where stopping is possible are listed.

Discontinuation Criteria (Safety Considerations)

Eligibility criteria

k	2	4	5	6	8	9	10	12	13	14	15	16	18	19	20	21	23	24	25	26	27	28	30
b	2	3	3	3	4	4	4	5	5	5	5	5	6	6	6	6	7	7	7	7	7	7	8

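### Children's gut staging omits the adult severe-pain criterion, so by the staging table alone the same gut picture is grade III in an adult but grade 0 or II in a child with low stool volume

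*Combined protocol and SAP*

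**What the plan says.** The Synopsis (Primary Endpoint) defines the primary endpoint as the incidence of grade III/IV acute GvHD by Day +100. The Synopsis hypothesis and section 1.0 predict that it will be below 10%. The Synopsis (Subject Population) covers "Pediatric and adult patients up to 35 years old", and section 3.1 admits participants older than one month, so both age columns of the staging table can be used.

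Appendix A states: "The modified Keystone criteria will be used for acute GvHD scoring for both pediatric and adult participants". Article II then stages the gut in two columns:

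- Adults: stages 0 to 3 go by daily volume (stage 1 also by biopsy-supported nausea), and stage 4 is "Severe abdominal pain with/without ileus" with no volume attached.
- Children: stage 0 is "< 10 mL/kg/d diarrhea", stage 1 is "10 - 15 mL/kg/d diarrhea, or persistent nausea with histologic evidence", stage 2 is "16 - 20 mL/kg/d diarrhea", stage 3 is 21-25 mL/kg/d and stage 4 is "> 26 mL/kg/d diarrhea".

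Article I converts gut stage 1 to grade 2 and gut stages 2 to 4 to grade 3. It has no gut entry at grade 4.

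Two provisions lie outside the tables. One begins "If the criteria are not met but clinical signs and symptoms are consistent with GvHD and systemic therapy was begun"; in that case acute GvHD may be diagnosed, and the scoring team stages the organ by symptom severity, guided by the NIH organ score for chronic GvHD. The other is a note to Article I that allows grade 4 with lesser organ involvement when performance status has fallen very markedly.

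Footnote §, attached to both gut columns, says that paediatric stool volume should be scaled to body surface area.

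**The concern.** One grading system is meant to serve both age groups, yet a clinical sign that alone puts an adult at the top gut stage counts for nothing in the children's column. Children move through stages 2 to 4 on volume only. If a child has severe abdominal pain and passes little stool, the table gives a low stage. The boundary between grades II and III decides whether a patient counts as a primary endpoint event, and for this picture the two columns fall on opposite sides of it.

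The children's column has two further faults. Its bands are not contiguous, and one of the gaps lies on the grade II/III boundary. Its unit, mL/kg, also disagrees with the table's own footnote. With 30 recipients, a single change of classification is visible in the reported incidence.

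**Working it through.** The plan gives no figure to reproduce here, so the check applies the tables as printed.

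**Inputs.** Gut stages come from Appendix A Article II, conversion to grade from Article I, and the sample size of 30 from section 12. Read literally, the adult stage 4 cell requires pain and makes ileus optional. The comparison is therefore between an adult and a child who both have severe abdominal pain and no other organ involved.

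**Step 1: table lookup.**

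| Patient with severe abdominal pain, gut only | Volumes checked | Gut stage | Grade |
|---|---|---|---|
| Adult | 0, 300, 700 mL/d | 4 | 3 |
| Child | 0, 5, 9.9 mL/kg/d | 0 | 0 |
| Child | 10, 12, 15 mL/kg/d | 1 | 2 |
| Child | 16, 20 mL/kg/d | 2 | 3 |
| Child | 25 mL/kg/d | 3 | 3 |
| Child | 27 mL/kg/d | 4 | 3 |

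The adult is grade 3 at every volume. The child first reaches grade 3 at 16 mL/kg/d. At 15 mL/kg/d or less the child is grade 0 or 2. If the adult criterion also stood in the children's column, this child would be stage 4 and grade 3 at any volume.

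**Step 2: routes outside the tables.**

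- Fallback: it needs the criteria to be unmet and systemic treatment to have been started. A treated child below 10 mL/kg/d meets no gut criterion, so the team may stage by severity and could reach stages 2 to 4, which is grade 3. A child at 10-15 mL/kg/d, or with biopsy-supported nausea, already meets stage 1, so the fallback arguably does not apply. An untreated child is outside it altogether.
- Performance-status note: this can give grade 4 but is permissive.
- Another organ: liver stage 2 or higher, or skin stage 4, gives grade 3 or 4 regardless of the gut.

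**Step 3: effect on the primary proportion.** For m children reclassified, the change is m/30: 1/30 = 3.3 points, 2/30 = 6.7 points, 3/30 = 10.0 points. For example, one case separates 2/30 = 6.7% from 3/30 = 10.0%. Neither the number of children among the 30 nor the frequency of this picture is given, so m cannot be estimated.

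**Step 4: band gaps in the children's column.**

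| Gap (mL/kg/d) | Neighbouring stages | Grades | Effect on endpoint |
|---|---|---|---|
| 15-16 | 1 and 2 | 2 and 3 | Can change event status |
| 20-21 | 2 and 3 | 3 and 3 | None |
| 25-26, including exactly 26 | 3 and 4 | 3 and 3 | None |

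A value midway in the first gap, (15 + 16)/2 = 15.5, has no stage. Exactly 26 has none even with whole-number recording.

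**Step 5: footnote against column.** Footnote § calls for scaling to body surface area, whereas the column scales by weight. No conversion is given, so the two instructions cannot both be followed.

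**The case against.** The strongest reply is that Appendix A already provides for patients whom the table does not fit. The fallback lets the scoring team stage a treated child by severity, and the performance-status note can lift the grade further. This stands against a reading that a reader might draw from the table, namely that such a child necessarily scores below grade III and is missed. The documents do not support that. It does not remove the problem, because an adult gets grade III from the table while a child needs a judgement. That judgement depends on treatment having been started, borrows a chronic GvHD score, and is arguably unavailable once stage 1 is met. In an open, single-institution study, this is a weak footing for a primary endpoint.

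A reader might also infer that the omission flatters the primary result. Relative to the adult rule it can only lower a child's table-based grade. A bias in the reported incidence would also require that such children occur, that the team does not upstage them and that no other organ gives grade III/IV. The documents establish none of these. The below-10% figure is a prediction, and section 12 attaches no test or success rule to it.

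Nor does section 12 compare adult and paediatric rates: it mentions separate analyses as a possibility if numbers allow. The grade IV stopping rule in section 10.2 is not affected through gut stage, because Article I has no gut entry at grade 4.

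The band gaps are largely a rounding convention, which the adult gut column (999/1000) and the liver column (3.0/3.1) share. That is fair, but the plan states no rounding rule, and the 15-16 gap lies on the endpoint boundary.

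Finally, the source of the modified criteria is not in the documents, so the difference may be deliberate. The row shows one entry per column, although a merged cell lost in reading the PDF cannot be fully excluded.

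**Conclusion.** The point holds in a limited form. By the Article II table alone, a child with severe abdominal pain and stool volume of 15 mL/kg/d or less is gut stage 0 or 1, hence grade 0 or II. An adult with the same picture is stage 4, hence grade III. The child reaches grade III/IV only through the discretionary fallback, the performance-status note or another organ. The primary endpoint is therefore not defined on the same scale across ages, and it can under-count severe cases in children.

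Each child affected is 3.3 percentage points of the primary incidence. How many would be affected is unknown. The conclusion assumes that the children's column is complete as printed and that severe pain can accompany low stool output in a child; the documents do not address the latter. It is worth correcting before analysis because it concerns the definition of the primary endpoint.

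**What to change.** 1. Reconcile the adult and paediatric gut stage 4 definitions in Article II so that the pain criterion applies in both columns, or state that the difference is intended and justify it.
2. Make the children's volume bands contiguous, or state a rounding rule, so that every value maps to one stage. The 15-16 mL/kg/d gap matters most; exactly 26 also needs a stage.
3. Reconcile the mL/kg column with footnote §, so that one scaling of paediatric volume remains. Closing the bands without this step would leave the column contradicting its footnote.
4. State the age at which a patient moves from the children's to the adults' column, since the table gives none.

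The cost is an edit to one table column and its notes. No new data collection is needed. The investigators must settle which stage each boundary value belongs to and whether the stage 4 difference was intended.
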